4.9 Sample Size and Power

The sample size of main parts of the study is dictated by previous studies and by practicality. Previous power calculations suggest that even using even well-defined clinical measures, the sample size for therapeutic trials will be more than 100 subjects, even using selected cohorts (9-13). However, the tests performed in the present study generally show robust differences between FRDA subjects and controls, and should provide more sensitive measures of disease if they retain sufficient fidelity in children. A sample size of 110 subjects should allow us to assess the independent effects of age, sex and genetic severity (GAA length) on measure results, facilitating a true understanding of the degree they can be used in children. One hundred subjects is also practically the upper limit of intervention studies in rare disease, and thus is appropriate for this study. In the present, study subjects will return every year for MEP and CrCEST, and every six months for clinical testing and blood tests through 36 months. MEP and CrCEST will have smaller samples size (30 and 12 respectively) as they are more precise but more labor intensive tests. Total duration for each subject is approximately 3-4 years, and initial recruitment will occur over a 2 year period. In the present study the goal is to define how each of the tests change over time in children with FRDA, and the factors (age, GAA length) that predict such changes. Each marker has been differentiated from control values previously; however, here control subjects will be used only if needed to confirm the differences, to provide a context and to be sure that tests perform similarly in all sites as a quality control measure.

5 STUDY ADMINISTRATION

5.1 Data Collection and Management

The study will use a database constructed through the University of Rochester for the FACOMS study. The University of Rochester database is compatible with the federal regulations for clinical trials. The University of Rochester also acts as the data center for many other neurological diseases, such as Parkinson's and Huntington's.

We will use CRFs compatible with this database. The CRFs do not ask for subject name, social security number, address or telephone number. The CHOP PI and coordinator will maintain a password protected list of this information which does not leave CHOP. The University of Rochester or others will not have any access to subject's name, address or contact information.

In addition to the data collected at each study visit, study data will be supplemented by the FACOMS study (IRB #01-002609). This will include data created on, before, and after the date of initial IRB submission (8/31/2017). For participants enrolled in FACOMS and who have consented for that study's data sharing component, data collected from #01-002609 prior to enrollment in the current (#14390) study may be shared with the current study. Data from overlapping study procedures will be shared from study #01-002609 to the current study #14390. This specifically includes data from the following performance measures:

medical history review, FARS, T25FW, 9HPT, extended timed walks, PedsQL and FARS ADL questionnaires. Other sites (UCLA, University of Florida) will handle data in the same manner.

The CHOP site will continue to maintain paper copies of all CRFs for three years following completion of the study.

5.2 Regulatory and Ethical Considerations

5.2.1 Risk Assessment

Clinical outcome measures (ataxia scales, speech testing, auditory testing, vision testing, timed walks, and peg test), questionnaires are non-invasive and are very similar to standard clinical evaluation. The risks to all aspects of the study are minimal and include fatigue and boredom. There is a small risk a participant may fall and be injured when trying to complete the walking tests; however this risk is minimal. Assistive devices may be used to complete these tasks, and study staff will be present to supervise and assist.

A standard venous blood draw of up to 40 mls is of minimal risk for a person 40 lbs or more. There is a risk of pain at the insertion of the needle, this is only for a short time. There are low risks of fainting and infection. All venipunctures will be performed by a trained phlebotomist or equivalently trained study coordinator or nurse. All precautions will be taken to reduce the risks. No adverse events are expected.

The risks associated with the blood tests are directly related to confidentiality. All samples will be labeled with a unique identifier. Laboratory personnel handling the patient samples and performing the genetic studies will not have access to subject personal identifiers.

When any data is published all identifiers will be removed. When data or resources are shared with other study PIs or collaborators no personal identifiers will be shared.

For participants undergoing CrCEST and bone strength sequences, the main risk to study participation is related to MRI scanning. Risk is minimized with telephone screening for contraindications to MRI, screening in-person at the study visit via detailed medical record review, as well as testing for metal-based objects before any MRI procedures. In addition, all participants are screened for any condition that may affect their safety and wellbeing during the study via careful medical record review. The study team will also closely monitor patients before, during, and after study procedures (e.g., follow-up).

MRI is the least invasive of all imaging modalities, and there are no known risks from MRI examinations provided subjects are carefully screened for contraindications. Two potential sources of concern lie in the strength and duration of the radio frequency pulse and of gradient pulses. These effects are the subject of very close study by the FDA, and the Siemens Verio Avanto, Sonata & Trio, Siemens is carefully manufactured (with both software and hardware interlocks) so that it is not possible (even by accident) to exceed the FDA guidelines. MRI is listed by the FDA as approvable as a non-significant risk device, and the studies themselves are of minimal risk. The effects of MRI on an unborn baby are unknown. We will therefore exclude pregnant women. An MRI has the potential to identify incidental findings. During the study visit, if a participant is found to have any previously unknown medical conditions, they will be referred to their primary care physician or metabolic physician for care. The Children's Hospital of Philadelphia MRI protocols and safety measures will be observed.

In the MEP procedure the main risk is associated with the safety and tolerability of TMS application. There are more than 100 published studies with reports of TMS applied to more than 800 normal and more than 300 neurologically abnormal children (most receiving single

or paired-pulse TMS). No serious adverse events have ever been reported in this population, suggesting that single pulse TMS in children is a minimal risk procedure. A 2009 report from the Safety of TMS Consensus Group specifies single pulse studies as minimal risk and offers further discussion of the safety of TMS in pediatric populations (14). Single pulse TMS is used as a clinical procedure in children with epilepsy, brain tumors, or other neurologic disorders for mapping of the primary motor cortex. The main safety concerns regarding TMS are the potential for provoking seizures, the potential to effect hearing, and pain or discomfort.

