- g) The Pediatric Quality of Life (PedsQL) and the FARS ADL scores. Subjects aged 2-7 inclusive will not need to complete a PedsQL scale. The PedsQL scale is the Pediatric Quality of Life Inventory. This scale has two separate questionnaires: one is designed for subjects between the ages of 8-12, the other for subjects between 13-18. The subject will answer the questionnaire with the help of the study coordinator. The subject's parent or guardian will also answer a separate questionnaire on the same topic. The FARS ADL score is a similar questionnaire asking the participant how they view their performance on tasks such as dressing, bathing, etc. Subjects and their guardians will be asked to complete questionnaires annually.

In some situations, such as a global pandemic, travel restrictions, as well as poor health or an overall concern for safety, it may not be possible for subjects to have an in-person visit every year. Under these circumstances, for subjects who have previously consented for this study it is possible to conduct a visit remotely via phone or video/telehealth. A remote visit will not include the 9HPT or any sample collection. Remote visits can include the following: review of consent forms, medical history and medications, completion of questionnaires that can be mailed or emailed to subjects, certain assessments of gait and motor functioning including answers to the surveys which ask questions about gait and motor abilities, parts of the FARS exam (for example, the Bulbar facial nerve function exam which can be performed and viewed over video), and timed standing and/or walking tests that can be viewed over video (provided that it has been determined ahead of time to be a low fall risk to the subject - fall risk will be determined by taking a recent detailed fall history of each subject prior to any standing or walking test).

All procedures detailed above (except the BBS and TUG) have been included on other IRB approved studies at CHOP, including a currently open study (IRB 01-002609).

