5.6 Confidentiality

Enrollment or non-enrollment in the study will not affect the patient's clinical care in any way. All participation is voluntary. Subjects who are non-ambulatory, more severely affected, or who have cardiomyopathy will not be asked to complete the timed walks. All study team will use a CHOP approved video platform to conduct these visits remotely to maintain subject confidentiality All data will be kept confidential except as required by law and kept in a secure data at the Children's Hospital of Philadelphia. All source documents will be stored in locked cabinets with access only for the principal investigator and co-investigators. Patients will be identified by identification numbers not by personal identifiers. Patient names will be anonymized in publications and only the personnel involved in the studies will be able to link results with patient names.

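### Section 5.2.1 promises staff on hand to assist at the walking tests, but 4.1 permits these tests over video and the supplied text requires nobody within the participant's reach

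*Combined protocol and SAP*

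**What the plan says.** Section 5.2.1 (Risk Assessment) identifies the hazard: "There is a small risk a participant may fall and be injured when trying to complete the walking tests". It calls that risk minimal and gives two mitigations in one sentence: "Assistive devices may be used to complete these tasks, and study staff will be present to supervise and assist". Nothing there separates clinic visits from remote ones.

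Section 4.1 (Neurological Outcome Measures) lets a participant who has already consented have a visit by phone or video when attendance is not possible. The permitted content includes "timed standing and/or walking tests that can be viewed over video", on condition that the test was judged beforehand to carry a low fall risk. The basis for that judgement is stated: "fall risk will be determined by taking a recent detailed fall history of each subject prior to any standing or walking test".

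Section 5.6 (Confidentiality) adds two relevant sentences. One limits who walks: "Subjects who are non-ambulatory, more severely affected, or who have cardiomyopathy will not be asked to complete the timed walks". The other says how remote visits are run: "All study team will use a CHOP approved video platform to conduct these visits remotely".

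The MRI paragraph of 5.2.1 also contains general wording on safety: "all participants are screened for any condition that may affect their safety and wellbeing during the study via careful medical record review" and "The study team will also closely monitor patients before, during, and after study procedures".

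**The concern.** The risk section relies on staff being able to help physically, and the remote-visit provision removes that help without replacing it. Participants have a progressive ataxia and may enter at age 2. Someone judged to be at low risk can still lose balance, and at a home test nobody is required to be close enough to catch them. A guardian will often be in the house, but the supplied text does not make that a condition of testing. The risk section therefore describes a protection that the plan's own procedures allow to be absent. What is at stake is participant safety and the accuracy of the risk description, not inference.

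**Working it through.** No plan figure needs reproducing, and no error rate or sample size is involved. The check sets the texts side by side.

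**1. Does 5.2.1 promise physical help at the walking tests?** Yes. The sentence follows directly from the fall risk and names both supervision and assistance. It has no in-person qualifier.

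**2. Can the same kind of test take place without staff in the room?** Yes. Section 4.1 allows timed walking tests over video, and 5.6 confirms that the study team works through a video platform.

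**3. Can the promise be kept by video?** Only in part. A generous reading of presence could include a video link, and supervision works that way. Assistance does not.

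**4. Do the other safeguards fill the gap?**

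| Safeguard | Where | What it does | Puts a person within reach? |
|---|---|---|---|
| Low fall risk, from fall history | 4.1 | Selects who is tested | No |
| Exemption from timed walks | 5.6 | Selects who is tested; does not mention standing tests | No |
| Record screening and close monitoring | 5.2.1, MRI paragraph | Selects and watches | No |
| Assistive devices | 4.1 and 5.2.1; not barred remotely | Gives support | No |

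**5. Is another adult required anywhere?** Not in the supplied text. Parents and guardians appear for permission and consent (3.4.1, 5.4) and for questionnaires (4.1), not as attendants at a remote test.

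**6. Whom must a remedy cover?** Entry is at 2 to 18 years (3.4.1). Follow-up is three years (3.3.1) or roughly three to four (4.9). For a participant entering at 18:

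- 18 + 3 = 21 years at the end of follow-up under 3.3.1
- 18 + 4 = 22 years at the upper end of 4.9

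Some participants will therefore be adults at later visits, and a rule that relied on a parent would miss them.

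**7. Scope.** The 5.2.1 sentence concerns walking tests only. Section 4.1 admits standing tests remotely under the same fall-history check, so a remedy placed there should cover both.

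The expected number of unattended tests or falls cannot be calculated, because the documents give neither a remote-visit share nor a fall rate.

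**The case against.** The best reply is that 4.1 is the specific rule for remote visits and 5.2.1 describes the ordinary clinic visit. The authors plainly saw the hazard of falling at home and chose to control it by selection: a prior fall-risk judgement, together with the exemption in 5.6. Remote visits are a contingency, walking tests are an optional part of them, and nothing shows that very young children would do timed walks at home. On this reading the only defect is a missing cross-reference, and the adult-within-reach rule is a preference. The consent pages were also removed, and families may be told there to keep a parent beside the child.

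Much of this is fair. It limits the point to a minor one, and the possible consent-form instruction is a real reason for caution. Whether selection alone is enough for a screened walker is a judgement the documents cannot settle. Still, reading 4.1 as the governing rule leaves the mitigation in 5.2.1 undelivered at remote tests. A qualifier in 5.2.1 alone would make the text consistent, but it would leave nobody required nearby.

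**Conclusion.** The concern holds as a minor safety and consistency gap. Section 5.2.1 offers assistance that cannot be given over video, and no supplied section substitutes anyone for the absent staff. The gap itself alters no endpoint or analysis. Its size is unknown for want of inputs; the only supported figure, an oldest age of about 21 to 22, bears on the scope of the remedy and not on harm. Confidence is moderate, because the conclusion assumes that no adult-presence instruction stands in the consent pages, which could not be checked.

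**What to change.** Add a short rule to the remote-visit text in 4.1:

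- For participants of any age, a remote standing or walking test goes ahead only while a parent, guardian or other capable adult stays within reach throughout.
- That adult neither touches nor paces the participant unless balance is lost.
- Before each test, staff confirm on video that the adult is in place and record this.
- If no such adult is available, the test is recorded as not done.

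In 5.2.1, keep the statement on assistive devices, limit the promise of staff assistance to in-person walking tests, and refer to 4.1 for remote ones. If the consent form already gives this instruction, repeat it in 4.1. Section 5.6 needs no change.

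The cost is small but not nil. A few remote tests will be lost, including some in low-risk participants over 18 who have no one with them. A nearby adult may slightly influence performance on walks done at maximum pace, which would make remote results a little less comparable with clinic results; the no-touch, no-pacing condition limits this without removing it. Beyond that, the change takes one field on the remote-visit form and a routine amendment.

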5.2.2 Potential Benefits of Study Participation

This study will provide long-term data on quantitative measurements of disease progression in children that will provide natural history data for FRDA. This study will also test and validate a non-invasive approach to measuring frataxin protein which will be necessary for future clinical trials. It will also seek to identify metabolic and anatomical biomarkers required for clinical trials. Lastly, this proposal will further develop the infrastructure and support for evaluating new clinical outcome measures and biomarkers. Subjects will not benefit directly but their participation will contribute to the necessary clinical research required to support the advancement of therapeutics in FRDA.

5.2.3 Risk-Benefit Assessment

The risks are minimal and given the potential benefits, the risk/benefit ratio is therefore extremely small.

5.3 Recruitment Strategy

Subjects will be recruited from multiple sources. A substantial number will be recruited from the ongoing natural history study of all ages, FACOMS, in which some children are already enrolled, and from the new diagnoses presenting to the sites. The FACOMS study collects detailed data on phenotype, neurological testing, medical history, and genetic severity; this data is available for the present work, and the present study will extend it by adding new tests and addressing new age groups. [name] alone sees 30 new FRDA patients per year, most of them children. The other two sites (University of Florida and UCLA) will also recruit through their practices' new patients and their FACOMS participants. In addition, study advertisements will be sent through the FARA registry. This database includes names of > 2000 FRDA pts worldwide, including 141 children living in the USA.

5.4 Informed Consent/Assent

The principal investigator and clinical coordinator will obtain informed consent or assent and parental consent from potential participants.

5.5 Payment to Subjects/Families

Participants will not receive financial rewards or inducements. There is also no cost to participation in the study. Participants who receive clinical care from any investigator or participating research sites, including the Children's Hospital of Philadelphia, will be responsible for those charges, as they are separate from the study.

Funds are available to reimburse some travel and hotel costs for all individuals traveling to the study sites. Our grant does provide funds to reimburse travel expenses up to \$500 per visit for participants. This must be arranged with the study coordinator prior to your arrival, and will require an IRS Form W-9. Only full name and social security number will be

collected on the W-9 form. Participants will receive reimbursement checks within 8 weeks after each visit.

5.6 Confidentiality

Enrollment or non-enrollment in the study will not affect the patient's clinical care in any way. All participation is voluntary. Subjects who are non-ambulatory, more severely affected, or who have cardiomyopathy will not be asked to complete the timed walks. All study team will use a CHOP approved video platform to conduct these visits remotely to maintain subject confidentiality All data will be kept confidential except as required by law and kept in a secure data at the Children's Hospital of Philadelphia. All source documents will be stored in locked cabinets with access only for the principal investigator and co-investigators. Patients will be identified by identification numbers not by personal identifiers. Patient names will be anonymized in publications and only the personnel involved in the studies will be able to link results with patient names.

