1 BACKGROUND INFORMATION AND RATIONALE

1.1 Introduction

Friedreich's ataxia (FRDA) is a rare autosomal recessive degenerative disorder characterized by ataxia, dysarthria, sensory loss, diabetes and cardiomyopathy. FRDA is a progressive neurodegenerative disorder with a prevalence of about 1 in 50,000 persons in the United States. The discovery of the abnormal gene in FRDA and its product (frataxin) has provided insight into possible pathophysiological mechanisms in this disease (1-3). An expanded GAA triplet repeat is found in both alleles of the FRDA gene in 97% of people with FRDA. This triplet repeat is located within an intron, leading to decreased RNA transcription and decreased levels of frataxin. While the basic-science-related understanding of FRDA has advanced rapidly, translational and clinical research has moved much more slowly. This reflects two aspects of FRDA. First it is uncommon-even large academic medical centers may only follow 10- 20 patients with this disorder. This requires that, in any clinical or translational study, multiple centers collaborate and assess patients in a coordinated manner. Secondly, until recently, quantitative tools for clinical assessment of FRDA have been unavailable. This has limited the ability of translational approaches to move forward and the initiation of therapeutic trials. Using recent support from the MDA and FARA, a group of investigators collaborated on development of clinical measures that can quantitatively assess FRDA (4). While a large amount of measure refinement remains to be performed, the data from their collaboration provides a framework for further investigation and for creating a network for performing further clinical and translational research including clinical trials. Still a major deficiency is the relative lack of sensitivity of measures in children, and their correlation with potential biomarkers.

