3.4.2 Exclusion Criteria

- 1) Inability to complete study evaluations
- 2) Severe cardiomyopathy/congestive heart failure (for MEP)
- 3) A pacemaker, any metal-based medical or non-medical implants/devices, any non-removable metal-based object (e.g. body piercings, jewelry, etc.) (for the CrCEST measures only)
- 4) Any history of intraocular injury or fragment in or around the orbit that cannot be cleared through radiologic evaluation (for the CrCEST measures only)
- 5) Any history of bullet, shrapnel, or stabbing wounds that cannot be cleared through radiologic evaluation (for the CrCEST measures only)
- 6) Claustrophobia or any known medical conditions which can be exacerbated by stress, anxiety, or panic attacks triggered by enclosed spaces (for the CrCEST measures and MEP only)
- 7) Inability to lie flat on a patient bed in an MRI machine for up to 90 minutes (for the CrCEST measures only)
- 8) Pregnancy (for the CrCEST measures and MEP only)

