4.7 Primary and Secondary Endpoints

The primary goal of this study is to gather long-term serial quantitative clinical data using the measures validated during the three years of the study.

Aims 1: The primary endpoint (s) are the change in each of the clinical measures over time. The rate of change of each of these will be compared for responsiveness to change (SD of change/mean change).

Aim 2: Biochemical measures: The rate of change of frataxin and each platelet biomarker will be determined as primary endpoints. The rate of change over time will be determined to define which measures are most sensitive to disease progression.

Aim 3: Anatomical measures: The primary endpoints are the post exercise recovery time, Tau, for CrCest and the MEP size for MEP testing. The rate of change over time will be determined to define which measures are most sensitive to disease progression.

The secondary analyses are:

The rate of change of each measure the (neurological measures, biochemical measures and anatomic measures) as a function of age, GAA repeat length and sex, as determined by linear regression models

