4.8 Statistical Methods

Aim 1: Results will be summarized with standard descriptive statistics using parametric or non-parametric methods, as appropriate given the variable distributions. Each of the parameters tested here have been abnormal in FRDA patients previously, including children. However, the specific features of how they behave in large pediatric cohorts is unclear. Thus, the most important analyses will be how the tests behave over time and how they reflect disease severity. Data for test-retest for the first 5 subjects at the primary site will be evaluated by determining the coefficient of variation over the tests. This will be performed immediately after study initiation as a separate analysis to confirm that the initial protocols have sufficient reproducibility to be useful. Full data collection will then proceed. Data from measures that were repeated (timed walks, TUG, CCFS tests) will be analyzed as means of the repeated tests and test retest features between trials. CCFS values will be analyzed as each hand separately (dominant vs non dominant) and hands together. Each test will be assessed in regression or mixed linear models accounting for age, sex and GAA repeat length. In addition the change over time will be established as well as the reproducibility of that change.

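### The timed walks are waived for more affected children, yet their responsiveness is compared with measures that carry no such waiver, and no common comparison set is defined

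*Combined protocol and SAP*

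**What the plan says.** The abstract (Study Measures) and section 3.1.2 schedule the 25-foot, 1-minute and 6-minute walks for all participants at every visit. Section 5.6, under Confidentiality, then states: "Subjects who are non-ambulatory, more severely affected, or who have cardiomyopathy will not be asked to complete the timed walks". The sentence after it concerns the video platform for remote visits. Section 5.6 gives no threshold for greater severity and does not say when status is judged.

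For Aim 1, section 4.7 says "The primary endpoint (s) are the change in each of the clinical measures over time" and "The rate of change of each of these will be compared for responsiveness to change (SD of change/mean change". Section 4.8 says "the most important analyses will be how the tests behave over time and how they reflect disease severity" and, on the model, "Each test will be assessed in regression or mixed linear models accounting for age, sex and GAA repeat length".

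Four other places bear on who walks:

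- Section 3.4.2 excludes "Inability to complete study evaluations", without saying how this fits with enrolled children who are excused the walks.
- The cardiac exclusion for MEP is limited to the severe form, "Severe cardiomyopathy/congestive heart failure (for MEP". The walk waiver names cardiomyopathy without qualification, and section 1.1 describes the disease as "characterized by ataxia, dysarthria, sensory loss, diabetes and cardiomyopathy".
- Section 4.1 allows assistive devices in the extended walks.
- At remote visits, section 4.1 permits walks over video only if fall risk is judged low, drops the 9HPT and keeps only parts of the FARS.

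No section gives a rule for a walk not done, an assumption about missing data, or a common set of children and visits for comparing measures.

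**The concern.** The study exists to find which measures track progression in children. The waiver removes walk data partly because of the trait being tracked, while section 5.6 leaves FARS and the 9HPT untouched. If status is judged visit by visit, a child who worsens enough drops out of the walk data but stays in the FARS data. Children exempt from entry contribute no walk data at all.

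Two results are exposed. Mean walk decline, taken from children still walking, would tend to be too small. The responsiveness ratio would then compare a walk figure from milder children with a FARS figure from nearly everyone, so a difference between measures could reflect who was tested. The walks could be set aside for later trials on that basis.

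**Working it through.** The plan offers no figure to reproduce: section 4.9 rests the 110 children on previous studies and practicality, and no slope, SD or exemption rate is given. Everything below uses assumed inputs and shows the mechanism; it does not estimate this study. The plan's ratio is SD divided by mean, so a larger value means a less responsive measure.

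**1. Children still walking.** Assumed inputs:

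- baseline speed 1.4 m/s (SD 0.35) and residual SD 0.10;
- mean slope −0.10 or −0.25 m/s per year, slope SD 0.05, 0.10 or 0.15, baseline–slope correlation 0 or −0.5;
- visits at 0, 6, 12, 18, 24 and 36 months (section 3.1.2);
- permanent exemption once a severity index passes a cut-off, the index being walking deficit alone, or half that and half a second score correlated 0.6 with it;
- cut-off set so that 5%, 15% or 30% of children walking at entry are exempt by month 36.

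This gives 2 × 3 × 2 × 2 × 3 = 72 scenarios of 120,000 children. Share recovered = mean 36-month change in children still walking ÷ mean change in all who walked at entry.

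| Exempt by month 36 | Share of true decline: median (range) | SD/mean relative to full data: median (range) | Leaving out slope −0.10 with slope SD 0.15 |
|---|---|---|---|
| 5% | 97% (87–100%) | 1.01 (0.995–1.08) | 93–100%; at most 1.04 |
| 15% | 91% (67–100%) | 1.03–1.04 (0.996–1.32) | 81–100%; at most 1.15 |
| 30% | 84% (38–101%) | 1.11 (0.99–2.21) | 64–101%; at most 1.40 |

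The far ends (67%, 38%, 2.21) arise only where the slope SD exceeds the mean slope. There the share of children who walk faster over time is Φ(−0.10/0.15) ≈ 25%, which fits poorly with a progressive disease. The normal model also allows negative speeds, in up to 13% of children at month 36; flooring speed at zero barely moves these ranges.

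**2. Two equally responsive measures.** A different assumed model: severity SD 1, annual slope 0.25 (SD 0.15), measurement SD 0.4, slope–severity correlation 0 to 0.6, 400,000 children. With full data, walk and examination score both have a ratio of 0.96. With 20% of walks waived at month 36, the walk's ratio is 1.04–1.09 (8–13% worse) while the examination in all children stays at 0.96. Mean walk change falls from 0.75 to 0.63–0.69. On the same children the two agree again (1.09 v 1.10 at correlation 0.6).

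**3. Precision.** With 20% waived, n = 110 × 0.8 = 88. The 95% half-width for a mean/SD of 0.5 is 1.96 × √(1/n + 0.5²/(2n)): 0.198 at n = 110 and 0.222 at n = 88. This loss is modest; selection matters more.

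**4. Direction for cardiomyopathy.** If a share p is exempt from entry and declines f times as fast as the others, observed/true = 1/(1 − p + pf). At p = 0.20: f = 1.25 gives 1/1.05 = 95%, f = 1 gives 100%, and f = 0.8 gives 1/0.96 = 104%. This route biases the result only if those children decline at a different rate, and either way.

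**5. Mixed model.** On the inputs in step 1, a random intercept-and-slope model on all available walks recovers 98–99.8% / 93–99% / 78–98% of true decline at 5% / 15% / 30% exempt. It helps, but only partly.

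**The case against.** - **The partial remedy is already named.** Section 4.8 lists mixed models with age, sex and GAA length. This stands: the gap is an uncommitted choice, not a missing model. It does not answer the ratio comparison in section 4.7, which has no common set.
- **Scope is unsettled.** The waiver stands directly before a sentence on remote visits, where section 4.1 already limits walking by fall risk. If the waiver is confined to remote visits, fewer walks are lost. The exclusion in section 3.4.2 may also keep some children out, and assistive devices keep others walking. These points reduce the missing data by an unknown amount. Even on the narrow reading, walks are lost for reasons tied to severity.
- **The comparator is not complete either.** Remote visits drop the 9HPT and parts of the FARS. In a ranking simulation where the walk's true ratio was 10% better than that of a measure seen in every child, the mismatched comparison reversed the order in 20 of 48 scenarios and a common subset in 3 of 48. A reader might infer a 40% chance of a wrong ranking. Those are counts of cells in a chosen grid, at 15% and 30% exemption only, against an idealised comparator; they are not probabilities. With the second measure 10% better, neither comparison reversed the order.
- **Responsiveness among children able to walk is a legitimate target** for a descriptive study with no treatment comparison. That stands, but then it should be stated, and the other measures shown in the same children.

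**Conclusion.** The point holds in a limited form. The waiver and the ratio comparison, followed together, judge the walks in a generally milder subset than measures such as FARS. This tends to understate walk decline and make the walks look less responsive. On the assumed inputs the typical effect is small to moderate: a median 3%, 9% and 16% shortfall in decline at 5%, 15% and 30% exempt, with ratio inflation of about 1%, 3–4% and 11%. It grows as the slope SD approaches or passes the mean slope, and may be near zero if few children are exempt. The true size and the number affected cannot be derived from the documents.

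A reader might go further and infer that most of the walk decline would be lost, or that the Aim 1 endpoint is invalid. The documents support neither: the 38% figure needs an analysis of observed cases only, which the plan does not specify, and an extreme slope setting. Nor do they establish that the waiver applies at all visits or is reassessed at each one. Whether the waiver is clinically right is not judged here.

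**What to change.** In sections 4.7 and 4.8, leaving the safety rule untouched:

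1. Compute the responsiveness comparison on a common set of children and visits as well as on all available data. Report the number and baseline severity of the children contributing to each measure.
2. Of the two model options in section 4.8, make the mixed model on all available visits the main analysis of change. State that it only partly corrects severity-driven omission and recovers nothing for children exempt from entry.
3. Record at each visit why a walk was not done (for example non-ambulatory, more severely affected but walking, cardiac, remote visit or fall risk, other), so that items 1 and 2 can be interpreted.

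The abstract and sections 3.1.2, 3.4.2, 4.1 and 5.6 must be reconciled on who is asked to walk and when.

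The cost is one form field and some added analysis, with no new visits or tests. The common set is smaller, describes milder children and does not always restore the full-data order.

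Time to loss of ambulation, zero or worst-rank scoring, and separate reporting of children with cardiomyopathy are optional sensitivity analyses. Zero-scoring can overstate decline: on the inputs of step 1 it gave up to 187% of the true value at 30% exempt.
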